# A Pilot Study to Investigate the Benefits of a Cannabidiolic Acid Topical Cream for the Treatment of Restless Leg Syndrome

## **Synopsis:**

Restless Leg Syndrome (RLS) is multifactorial disease state with many different potential pathophysiological mechanisms, which includes dysfunctions from the cerebral cortex and spinal cord to mechanosensitive channels at the musculoskeletal periphery. Most therapeutic agents' effectiveness focuses on the CNS (e.g., dopaminergic drugs) or Renshaw cells. To our knowledge, therapeutic agents that are focused on the periphery were not very effective.

This technology focuses on the peripheral musculoskeletal component of the disease and is directed at treatment modalities that correct the dysfunction of mechanosensitive channels. By combining what is known about cannabinoids activity at the transient receptor potential channel of ankyrin 1 (TRPA1)² and the role TRPA1 plays in regulating the shape and rigidity of the surrounding membrane structure at the Piezo channels³, an effective therapy at the site of discomfort should emerge. Moreover, the lessening of membrane tension is imparted by molecules that readily penetrate the membrane⁴, which Chylobinoid, the topical active ingredient, is uniquely designed to do.

If successful, we will demonstrate, for the first time, an effective treatment for RLS with a topically applied medicine. This medicine will virtually eliminate the safety concerns associated with current RLS treatments. Moreover, to our knowledge, this potential medicine will represent the first time that mechanosensitive channels will be the target of a cannabinoid to treat a specific disease state.

#### Abstract:

Anecdotally, we have preliminary observed 4-5 individuals with moderate to severe RLS describing near complete resolution of sensorimotor symptoms after consistently topically applying Chylobinoid™ cream to the affected extremities. We endeavor to validate these non-clinical observations by setting up a clinical trial with appropriate statistical power to demonstrate Chylobinoid's effectiveness of improving symptoms associated with RLS relative to placebo.

Our clinical endpoints will be measured using the International Restless Legs Syndrome Rating Scale

- 1. Statistically significant improvement of symptoms
- 2. A Minimally Clinically Important Difference of 3-point reduction.

We will present the data at selected scientific meetings and, depending on the results, will publish the study in a peer-reviewed journal.

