## Participants and protocols:

Participants of both genders will be recruited. Participants with at least a three-month diagnosis of RLS without prior operative intervention will be approached for enrollment in the study. Participants will be enrolled once the trial is described, questions answered, and consent form signed. Pre-treatment IRLSSG scores are collected over the phone on new participant questionnaires. Anyone who does not meet the IRLS criteria for at least mild RLS with a minimum IRLS score of 7 will screen fail. Participants will then have the trial cream described, how to apply it (see below), and then the cream will be mailed to them. Once received, participants will use the cream at least once a night to the affected area(s).

The topical cream will be contained in a jar. The cream will be applied by hand from a measuring spoon and massaged into the skin. The participant will measure 1 teaspoon and apply this amount to each of the regions of the area the participant reports having RLS. Participants will be instructed to apply the topical cream once per day 30-45 minutes before bed for a total duration of two weeks. Participants will be instructed to re-apply the cream if they wake up and feel RLS symptoms.

Participants will receive a follow up phone call at the end of the 2-week study. Post-treatment IRLSSG and the PGIC (patient's global impression of change) will be collected at that time. That completes the study.

Sample Size: 10 participants

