## Primary outcome measure:

- 1. Statistically significant response to treatment using IRLSSG
- 2.A MCID of 3 using the IRLSSG

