### **Statistical Analysis Plan:**

The baseline and post-intervention observations of the IRLSSG will be calculated using the associated scoring rubric. The distribution of baseline scores will be subtracted from the distribution of post-intervention observations to yield a distribution of difference scores. A Shapiro-Wilk test will be performed on the distribution of difference scores to assess normality. If the assumption of normality is met, parametric paired-samples t-test will be performed to test for significant change in IRLSSG scores. Means and standard deviations will be reported and interpreted for the t-test analysis. If the assumption is violated, then a non-parametric Wilcoxon Signed Rank test will be performed to test for change in IRLSSG scores across time. Medians and interquartile ranges will be reported for the non-parametric test. The PGIC will be scored using its associated scoring rubric. Normality of the two questions from the PGIC will also be tested for using Shapiro-Wilk tests. If the distributions for the questions are normal, means and standard deviations will be reported, and if either or both distributions are non-normal, then medians and interquartile ranges will be reported. All analyses will be conducted using SPSS Version 29 (Armonk, NY: IBM Corp.) and statistical significance will be assumed at an alpha value of 0.05.

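### The Abstract claims appropriate power, and against placebo, for a single-group study of 10 with no stated basis; 80% power for 3 points needs an SD of change of about 3 or less

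*Protocol*

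**What the plan says.** The Abstract states that the aim is to set up "a clinical trial with appropriate statistical power to demonstrate" that the cream improves symptoms compared with placebo. It then names two endpoints on the IRLS scale: statistical significance, and "A Minimally Clinically Important Difference of 3-point reduction". The section Primary outcome measure repeats both, the second as "A MCID of 3 using the IRLSSG".

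Research Methods describes an open-label, proof-of-concept study, and the title calls it a pilot. No control group appears anywhere. Under Participants and protocols the size is one line: "Sample Size: 10 participants".

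The section Statistical Analysis Plan computes post-treatment minus baseline scores and says a "parametric paired-samples t-test will be performed to test for significant change in IRLSSG scores". The fallback is "If the assumption is violated, then a non-parametric Wilcoxon Signed Rank test will be performed". The level is fixed: "statistical significance will be assumed at an alpha value of 0.05". For output, "Means and standard deviations will be reported and interpreted for the t-test analysis"; medians and interquartile ranges replace them on the Wilcoxon branch.

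**The concern.** A pilot need not state a power, and silence on power would not be a finding here. This protocol does make a power claim, and nothing in it supports the claim. There is no SD, no effect the study was sized for, no target power and no reason for the number 10. The claim is also tied to a comparison with placebo that the design does not contain.

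What is at stake is how the result will be read. The Abstract plans presentation at meetings and possibly publication. A reader told that the trial was adequately powered will tend to take a non-significant result as evidence against the cream. The same reader will take a significant estimate at face value. Whether either reading is safe depends on the SD of change, which the protocol does not give.

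**Working it through.** **Inputs from the protocol.** n = 10 in one group (Participants and protocols). Alpha 0.05, paired t-test with Wilcoxon fallback (Statistical Analysis Plan). Threshold 3 points (Abstract; Primary outcome measure).

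**Assumptions.** The test is two-sided; the protocol does not say, but it tests for change. The SD of the difference scores is not given, so a range is shown. Difference scores are normal and all 10 complete. Change is written as the size of the reduction.

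**The plan's own figure.** The figure of 10 cannot be reproduced, because no power, SD or design effect is stated.

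**Placebo comparison.** The analysis compares each participant with his or her own baseline. With no placebo group, a difference from placebo cannot be estimated, so power for it is undefined at any n. What follows concerns only the before-after test.

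**Formulas.**
- Noncentrality = (true change / SD) × √10, with 9 degrees of freedom and critical value 2.262.
- Power = probability that a noncentral t variable falls outside ±2.262.
- 95% CI half-width = 2.262 × SD / √10 = 0.715 × SD.

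**A result that needs no assumed SD.** Power is 80% when true change / SD = 0.996. For 3 points this gives SD = 3 / 0.996 = 3.01.

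**Results by SD.** For example, at SD 4 the noncentrality is (3/4) × 3.162 = 2.372.

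| SD of change (assumed) | Noncentrality, 3 points | Power, 3 points | Power, 6 points | CI half-width (points) |
|---|---|---|---|---|
| 3 | 3.162 | 80.3% | >99.9% | 2.15 |
| 4 | 2.372 | 56.2% | 98.7% | 2.86 |
| 5 | 1.897 | 39.6% | 92.0% | 3.58 |
| 6 | 1.581 | 29.3% | 80.3% | 4.29 |
| 8 | 1.186 | 18.6% | 56.2% | 5.72 |

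At SD 2.5, power for 3 points is 92.0%.

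**Sensitivity, 3 points, SD 4 and 8.**
- Wilcoxon test (4,000 simulated trials per SD): about 55% and 18%.
- One-sided 0.05: 71% and 29%.
- Two-sided with 8 analysed: 45% and 15%. Some loss is possible, because the Adverse Events section stops participants who have a skin reaction.

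**What a non-significant result excludes.** It excludes a 3-point benefit only if the upper confidence limit is below 3. With an observed SD of 4, the mean reduction must be under 3 − 2.86 = 0.14 points. With an observed SD of 8 it must be under 3 − 5.72 = −2.72, that is, a mean worsening of more than 2.7 points. So non-significance alone is not enough.

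**Estimate given significance.** If the true change is 3 points, the mean estimate among significant trials is about 3.8, 5.0 and 6.2 at SD 4, 6 and 8 (simulation). These are about 1.3, 1.7 and 2.1 times the truth. If the true change is 6 points, the estimate is about 6.0 at SD 4 and 6.6 at SD 6, or 1.0 and 1.1 times.

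**The case against.** The strongest reply has four parts.

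- **The SD range is assumed.** A reader might infer that the trial simply has 19% to 56% power. The documents do not support that: those figures belong to an SD of 4 to 8, which the protocol does not give, and at SD 3 power is 80%. This objection stands, so the figures hold only under that assumption.

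- **Three points is not a stated design effect.** It is an endpoint threshold. Just before the power claim, the Abstract reports that four or five people with moderate to severe RLS had almost full relief, which suggests a hoped-for change well above 3 points. At 6 points, power is 80% or more up to SD 6; at 10 points it is 94% even at SD 8. This stands in part: the power claim is unsupported rather than shown false for every effect. But the protocol never turns the anecdote into a target effect, and 3 points is the only numerical effect it names.

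- **A null result is not worthless.** A reader might conclude that a negative trial would be uninformative, or that any significant result must be inflated. Neither follows. A null result could count against a large effect, and inflation is small if the true change is 6 points and the SD is 4 to 6.

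- **Interval reporting may belong in a separate analysis plan.** That is fair, and a missing interval is not in itself the fault here. An interval can also be rebuilt from n and the SD, provided the reported SD is that of the difference scores; the protocol does not say which it is. None of this rescues the Abstract's statement, which a later document cannot justify while the protocol gives no basis for 10.

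**Conclusion.** The claim of appropriate power is unsupported, and as a claim about placebo it cannot be met by a single-group design. For the before-after test, 10 participants give 80% power for 3 points only if the SD of change is about 3 or less. That rests on a two-sided test at 0.05, normal differences and 10 completers. If the SD is 4 to 8, an assumption, power for 3 points falls from about 56% to 19%, and the half-width runs from 2.9 to 5.7 points. In that range, non-significance alone would not exclude a 3-point benefit, and a significant estimate would tend to be too large if the true change is near 3.

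A reader might go on to infer that 10 is too few and the trial should be enlarged. The documents do not require that. Ten can be a reasonable number for a pilot; the fault is in what the protocol says that number can show.

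**What to change.** - **Abstract:** remove the wording on appropriate statistical power and, in the same sentence, the wording on comparison with placebo. Removing only the first would leave a comparison the design cannot make.
- **Participants and protocols:** state that 10 is a feasibility number and give the expected precision, a 95% CI half-width of about 0.72 times the SD of change. If the sponsor prefers to keep a power statement, it needs a stated SD, a target effect and the resulting power for the before-after change.
- **Statistical Analysis Plan section:** report the mean change with its 95% CI, or the median change with its interval if the Wilcoxon test is used. Judge the 3-point primary outcome by comparing that interval with 3.

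The cost is wording in three places, one extra output and a less favourable stated claim. No participants are added and no study procedure changes.

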### **Research Methods**

**Study design:** Prospective open-label proof-of-concept trial.

**Study Population**: Subjects must meet all of the enrollment criteria to be eligible for this study. Eligibility criteria may not be waived by the Investigator and are subject to review in the event of a Good Clinical Practice audit and/or health regulatory authority inspection.

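### The Abstract promises a powered comparison with placebo, but the trial has no placebo group and tests only change from baseline

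*Protocol*

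**What the plan says.** The Protocol's Abstract says the investigators are "setting up a clinical trial with appropriate statistical power to demonstrate" the product's "effectiveness of improving symptoms associated with RLS relative to placebo". This is the only mention of placebo in the document. The Significance section adds that the purpose of the work is to prove effectiveness in a clinical setting.

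The sections that govern conduct describe something else:

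- Research Methods gives the design as "Prospective open-label proof-of-concept trial".
- Participants and protocols has the trial cream explained to each participant, "and then the cream will be mailed to them". It describes no second cream, allocation or blinding. It also fixes "Sample Size: 10 participants".
- The Protocol's Statistical Analysis Plan section subtracts baseline from post-treatment scores. It tests the differences with a paired t-test, or with a Wilcoxon signed rank test if normality fails, at alpha 0.05. It contains no comparison between groups.

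**The concern.** The stated aim and the planned trial answer different questions. The aim asks whether the cream is better than placebo. The analysis asks whether scores changed over two weeks of use. A positive answer to the second is not an answer to the first.

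The outcome is self-reported by people who know they are using the product. Application also has a physical component: "The cream will be applied by hand from a measuring spoon and massaged into the skin". A fall in score could come from the cream, from placebo response, from natural fluctuation in symptoms or from the massage, and nothing in the design separates these.

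The Abstract plans presentation at meetings and possible publication. A significant result reported against the aim as written would claim a comparison that was never made, and a power that was never calculated.

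**Working it through.** **1. Aim against plan**

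| Element | Aim in the Abstract | What the Protocol sets up |
|---|---|---|
| Comparator | Placebo | The participant's own baseline score |
| On placebo | Some, by implication | 0 of 10 |
| Test | Cream against placebo | Post-treatment minus baseline, paired t or Wilcoxon |
| Power | Called appropriate, no number | No SD, target power or calculation |

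**2. What the planned test estimates**

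Write the mean change as τ + c, where τ is the effect of the cream and c is everything else that moves the score over two weeks. The paired test has the null hypothesis τ + c = 0. The aim concerns τ alone. With no placebo group, c is not estimated, so τ cannot be separated from it. Power for a test of τ has no definition in this design.

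**3. The plan's own figure**

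The sample size of 10 cannot be reproduced, because no inputs are given for it. The 3-point minimal important difference appears as an endpoint and is not tied to the number of participants.

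**4. Illustration for the test that is planned**

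- From the Protocol: n = 10; change of 3 points (Primary outcome measure, used here as a planning effect); alpha 0.05.
- Assumed: two-sided test, all 10 evaluable, normally distributed changes, SD of change from 3 to 8 points.
- Formula: λ = (3/SD) × √10; power = P(|T| > 2.262), where T is noncentral t with 9 degrees of freedom and noncentrality λ.

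| SD of change | λ | Power |
|---|---|---|
| 3 | 3.162 | 80.3% |
| 4 | 2.372 | 56.2% |
| 5 | 1.897 | 39.6% |
| 6 | 1.581 | 29.3% |
| 7 | 1.355 | 22.8% |
| 8 | 1.186 | 18.6% |

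Power of 80% needs a standardised change of 0.996, so for 3 points the SD may be at most 3/0.996 = 3.01. Read as one-sided 0.05, the threshold is 0.853 SD, and the largest SD is 3/0.853 = 3.52. For the Wilcoxon branch (exact, two-sided, simulated with normal changes) the threshold is about 1.02 SD.

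**5. Attribution**

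The test depends only on τ + c. The same table therefore gives the chance of a significant result when the cream does nothing (τ = 0) and scores fall 3 points for other reasons: 80.3% at SD 3, down to 18.6% at SD 8. The value of c is an assumption; the Protocol gives no basis for one.

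**The case against.** The strongest reply is that this is a pilot and is run as one. Placebo appears once, in introductory prose. The title, the design statement, the single cream, the primary outcome and the analysis all agree on an uncontrolled before-after study, and the Abstract's own two endpoints are not comparative. Nothing in conduct or data collection depends on the phrase. All of that stands, and it is why the remedy is small. It does not remove the point: the phrase sits in the statement of the aim, and the Significance section repeats the overclaim without the pilot's limits. A separate analysis plan could not help, since it cannot supply a control group.

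A reader might infer more than the Protocol supports:

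- **That 10 participants are too few.** This is not shown. The only effect information is anecdotal, 4-5 people "describing near complete resolution of sensorimotor symptoms", with no figure attached. It may imply a change well above 3 points, and the SDs above are assumptions.
- **That lacking a control group is itself an error.** An open-label single-group pilot is a legitimate design. The fault is the mismatch with the aim.
- **That the paired test is invalid.** It can keep its level for the hypothesis of no change. The difficulty is attribution, not type I error.
- **That all confident wording must go.** The Synopsis is conditional on success, and "Statistically significant response to treatment using IRLSSG" is common usage for change on treatment. Editing either is optional.
- **That sidedness and a confidence interval are missing.** Both may be left to a separate analysis plan.

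**Conclusion.** The point holds on the text alone. The aim names a comparison with placebo that the trial cannot make, since 0 of 10 participants receive placebo, and claims power for it that is undefined. A significant change from baseline would show that scores moved, not that the cream moved them, so it cannot prove effectiveness as the Significance section says.

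Power for the before-after test is unsupported rather than inadequate. The threshold of about 1 SD for 80% power depends on n = 10, a two-sided 0.05 paired t-test and full follow-up. Turning it into points needs an SD that the Protocol does not give.

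**What to change.** In the Abstract, delete the phrases on statistical power and on placebo, and state the aim as assessing the two-week within-participant change in IRLS score during open-label use. In the Significance section, replace the claim of proof with wording limited to an uncontrolled preliminary signal. Carry the same limit into the conclusions when results are presented or published.

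Design, sample size, phone calls and planned tests do not change. The cost is two sentences of rewording and a more modest stated claim.

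Keeping the placebo aim would mean a different trial. For a 3-point difference between groups, two-sided 0.05 and 80% power, n per group = 2 × (1.960 + 0.842)² × SD²/3². That is 16 per group at an assumed SD of 3 and 112 at an assumed SD of 8. Every operative section describes an uncontrolled study, so rewording is the smaller change and the one recommended.

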### Significance:

This technology focuses on the peripheral musculoskeletal component of the Restless Leg Syndrome (RLS), a poorly understood sensorimotor disorder, and is directed at treatment modalities that correct the dysfunction of mechanosensitive channels that contribute to RLS's presumed mechanism of action. Our hypothesis is that modulating activity of the Piezo channels and acting on the TRPA1 that regulate the Piezo channels are key target areas to treat the symptomology of RLS.

Thus, an effective therapeutic agent to treat RLS targeted to the musculoskeletal periphery would be one that possesses three key properties:

- 1. Is amphiphilic enough to effectively penetrate, and consequently modulate, Piezo channel associated membranes.
- Is known to modulate TRPA1.
- 3. Can introduce divalent cations to interfere with the increased calcium flux initiated by overstimulation of Piezo channels.

Chylobinoid is a magnesium infused cannabidiolic acid (CBDa)-rich micellar complex derived from hemp extract. The magnesium CBDa complex is polarity adaptive and that, combined with its micellar structure, imparts the measure of amphiphilicity desired for both relief of membrane tension with distortion of membrane structure and deep penetration through the epidermis to the target site. CBDa is also a potent TRPA1 ligand. Finally, introducing magnesium into the system will contribute to disrupting the calcium flux.

We have already demonstrated, anecdotally, the effectiveness of topically applied Chylobinoid in improving the symptoms associated with RLS. The work described in this protocol is to prove Chylobinoid's effectiveness in treating RLS in a clinical setting.

### **Research Methods**

**Study design:** Prospective open-label proof-of-concept trial.

**Study Population**: Subjects must meet all of the enrollment criteria to be eligible for this study. Eligibility criteria may not be waived by the Investigator and are subject to review in the event of a Good Clinical Practice audit and/or health regulatory authority inspection.

## Inclusion criteria:

- Patients with at least 3 month-course of symptomatic restless leg syndrome
- Must meet International Restless Legs Syndrome Study Group (IRLSSG) criteria of at least mild symptoms.
- Age > 18 years, including both males and females
- Patient provides informed consent

